9.3.3. Patient characteristics and potential confounding variables

9.3.3.1. Recorded in EPI-MAL-002 and EPI-MAL-003

For all enrolled subjects, socio-demographic characteristics, data on access to care and health care seeking behaviour, neighbourhood of residence (urban/rural area), distance from health facilities, use of malaria control intervention at individual level (e.g. use of bednets, indoor residual spraying, seasonal malaria chemoprevention), information on medication intake (including curative antimalarial drugs) during the 14 days preceding onset of symptoms, whether recorded (evidence of prescription) or reported (prescribed without any evidence or self-medicated) will be recorded in the eCRF. Information on medication given as treatment of an AESI, meningitis or malaria, information on medication given for chronic therapy, information on medication administered in anticipation of a reaction to the vaccination, and exposure to environmental hazards such as chemicals will also be recorded. Data on vaccination, more specifically, dates and doses of EPI vaccine administration, as well as data on medical history including co-morbidities (e.g. chronic diseases, such as known HIV infection), or diagnosed congenital

CONFIDENTIAL115055 (EPI-MALARIA-002 VS AME)
Protocol Amendment 7 Final

diseases, such as known hemoglobinopathies, will also be collected. In case of hospitalisation, type of health care facility will be collected.

For children enrolled in enhanced hospitalisation surveillance or hospitalised children in active surveillance, additional information on co-morbidities will be captured such as malnutrition, chronic diseases, known HIV infection status, known hemoglobinopathies.

Of note, the vaccine history will be ascertained for all enrolled subjects through the following channels: individual vaccination cards, vaccination registers at the health care facilities and vaccination data collected during study area census rounds. If any of the sources described here above confirm vaccination, it will be assumed that vaccination has taken place for the analysis.

9.3.3.2. Recorded in EPI-MAL-005

Malaria transmission intensity (MTI) data will be collected through EPI-MAL-005 (see Section 9.4.3 for more detail). Rainfall and humidity, where available, will be collected at the study area level. Bednet use, seasonal malaria chemoprevention and other malaria control measures will also be collected at the HDSS or equivalent surveillance system (population) and individual level (which will be summarized at centre level).

The *P. falciparum* parasite prevalence will be measured as a way to characterise the MTI. The *P. falciparum* parasite prevalence will be computed as the proportion of subjects infected with *P. falciparum* parasitaemia divided by the total number of subjects tested, and will be estimated through annual cross sectional surveys (study start, every 12 months, and study end) during malaria peak transmission, in subjects at least 6 months and less than 10 years of age at the time of survey. These estimates will be calculated for each year and for each site separately.

9.4. Data Sources

9.4.1. Health Demographic Surveillance System (or equivalent surveillance system)

Each HDSS or equivalent surveillance system site maintains a demographic database which is updated on a regular basis to include births, deaths, immigrations and emigrations. Data regarding vaccinations is also included in the study site database. This information is obtained through census rounds (at least once a year) and constantly updated in between the rounds with the help of key-informants living in the community. Cause of deaths is established by trained fieldworkers using the INDEPTH Standard Verbal Autopsy Questionnaire [INDEPTH, 2003] for children who died at home. From this database, the listing of children at the beginning of the study will provide the study site with a basis for recruitment of children <18 months old for active surveillance and for the total number of children < 5 years of age recorded at least once a year during the study duration. During the study, further newborns may be identified by one of several possible mechanisms (depending on the site): by subsequent HDSS or equivalent surveillance system updates, by existing community-based informers who report new births/deaths/other events to the study sites between censuses, at the time of first EPI

CONFIDENTIAL115055 (EPI-MALARIA-002 VS AME)
Protocol Amendment 7 Final

vaccination (e.g. BCG vaccination or first DTP/HepB/Hib vaccination), or at birth (if born at a health care facility).

If a site is not part of the INDEPTH network, or does not have an equivalent surveillance system in place, the INDEPTH procedures for demographic census and for verbal autopsy might be implemented to ensure consistency across study sites.

9.4.2. Active surveillance and enhanced hospitalisation surveillance of study EPI-MAL-002

Subjects enrolled in active surveillance will have data collected during home visits, outpatient visits and hospitalisations at all health care facilities, while subjects enrolled in enhanced hospitalisation surveillance will have data collected during hospitalisation only (see also study procedures in Section [9.2.7](#)).

The surveillance system should be embedded into all health care facilities (including community health care services and potential mobile teams) of the study area.

The first level of screening will be done at the community level during follow-up visits by study community health workers who will be trained to recognise signs and symptoms of AESI and meningitis. Any subject presenting with specific signs or symptoms, as described by the Job Aid tool, will be referred to the health care facility (usually primary care facility) where the public health care staff will perform clinical assessment according to routine practice (see Section [9.2.7.5](#)). If a suspected AESI, meningitis or severe malaria, including cerebral malaria, case is detected at the primary health care facility level, the subject will be referred to a higher level health care facility (hospital) to confirm the diagnosis based on the highest level of diagnostic certainty available (see [Annex 5](#)). If another event is detected at the primary health care facility level, the study participant might be referred to a higher level health care facility according to the routine practice. In the case of a seriously sick child, this child will be referred directly to the hospital by the community health worker.

Training on AESI and meningitis diagnosis, HIV and hemoglobinopathies will be provided and support will be available from specialised health care professionals to confirm diagnosis (see SPM for details) (see Section [9.2.7.6](#)).

The surveillance system will also be implemented in the study area at each health care level within the HDSS or equivalent surveillance system catchment area. Health care workers will record all outpatient visits (referral and non-referral) of subjects enrolled in the active surveillance up to the end of the active follow-up) on a register allowing for the collection of basic data (e.g. date of visit, clinical diagnoses and rapid testing confirmation, referral or treatment). In case appropriate registers are not available in the facilities, study registers should be developed. At enrolment, subjects participating in active surveillance will be given study specific stickers with the subject's study number. The stickers can be used on the health care facility's registers if no other system is in place to indicate a subject's visit and facilitate identification of data from enrolled subjects from the facility's register. The recorded data will be collected retrospectively on a regular basis and encoded in the eCRF.

CONFIDENTIAL

115055 (EPI-MALARIA-002 VS AME)
Protocol Amendment 7 Final

Every day, study staff will perform a round at hospitals and other health care facilities (with hospitalisation facility) to see all newly hospitalised children that could be eligible for the study. Parents/LARs of eligible children not yet enrolled into the study should be asked if they would agree to their child's participation and signed or witnessed and thumbprinted informed consent shall be obtained.

The monthly total number of hospitalised children < 5 years of age will be recorded in the logbook monthly for the study duration, for the purpose of the aggregated data analysis.

All enrolled hospitalised children will have their diagnosis recorded with main symptoms and results from routinely performed confirmatory tests. In the case of AESI and meningitis, additional information should be recorded according to clinical and laboratory standard of diagnosis (see [Annex 5](#)). Study staff will complete the eCRF containing all relevant information for each enrolled subject, to include an International Classification of Diseases (ICD) code allocated by a physician. All enrolled hospitalised subjects diagnosed with suspected AESI or meningitis will have a sample of approximately 5 mL of whole blood taken; in the case of neurological AESI or meningitis requiring a CSF sample according to routine practice, where possible, an additional aliquot will be reserved (for details refer to Section [9.2.7.3.1](#)). Admitted subjects are expected to receive care by hospital staff following National guidance. As part of good medical practice, the clinical staff will ensure that sick subjects admitted to hospital will receive adequate care provided by health care facilities (see Section [9.2.7.5](#)).

AESI, other AE leading to hospitalisation or death, meningitis, or malaria will be recorded in the eCRF. Data entry is described in Section [9.6](#).

The investigator will assess the maximum intensity (mild, moderate, severe) that occurred over the duration of the event for all AESI, other AE leading to hospitalisation or death, meningitis, or malaria reported during the study. The assessment will be based on the investigator's clinical judgement.

9.4.3. Study EPI-MAL-005

The RTS,S/AS01_E vaccine is expected to be introduced through national immunisation systems, and will lead to a reduction in the incidence of *P. falciparum* malaria in vaccinated subjects in EPI-MAL-003 when compared to baseline rates recorded in EPI-MAL-002. Annual fluctuations in malaria incidence occur as a result of changes in transmission intensity, which may be caused by changes in environmental factors such as rainfall or changes in usage of other malaria control interventions (use of bednets for example). Therefore, by taking into account these variations in MTI and malaria control intervention coverage, more accurate estimations of the vaccine impact on malaria disease using RDT and/or microscopy during EPI-MAL-003 will be possible.

In EPI-MAL-005, the following parameters will be assessed: estimates of *P. falciparum* parasite prevalence and of the use of malaria control interventions at community level, changes in environmental factors such as rainfall, changes in health care seeking behaviour, within-site geographical heterogeneity in MTI and individual malaria

CONFIDENTIAL

115055 (EPI-MALARIA-002 VS AME)
Protocol Amendment 7 Final

prevention measures and risk factors for clinical malaria. Compliance with DTP-based, measles and RTS,S/AS01_E vaccines will also be collected.

EPI-MAL-005 started in Q4 2014 and is planned to run in parallel with EPI-MAL-002 and EPI-MAL-003, in similar if not identical settings. Its primary objectives are to estimate the annual parasite prevalence and record malaria control measures, providing information on potential confounding factors relevant to interpreting EPI-MAL-002/003 outcome measures.

It may happen that subjects enrolled in EPI-MAL-002 are also enrolled in EPI-MAL-005. Cases of malaria detected only during the annual home visits planned for EPI-MAL-005 will not be included in the analysis of EPI-MAL-002. However, if the cases of malaria are detected during an EPI-MAL-005 home visit that coincides with a home visit scheduled in EPI-MAL-002, the events will be captured in EPI-MAL-002.

9.5. Study size

The study targets enrolling 15,000 children per group (i.e. 6-12 weeks group or 5-17 months group; with about 10,000 children of 15,000 in each group enrolled where the RTS,S/AS01_E vaccine will be implemented), for a total of 30,000 children with at about 20,000 children enrolled where the RTS,S/AS01_E vaccine will be implemented.

Burkina Faso sites are planned to early terminate any study activities by Q2 2019. As a consequence, the data from those sites will be presented in the progress reports up to Q4 2019, but none of those data will be part of the statistical analyses for the interim and final reports. There will be a full follow-up of about 10000 and not 15,000 children.

The co-primary objectives will estimate the incidence of AESI and meningitis. The precision of the estimate is related to the incidence and the period at-risk of these events following any dose (or equal point in time for 5-17 months group), with a censoring of the follow-up time when the subject receives the next dose. For some of the AESI the incidence could be very rare (around 1/100,000 person-years [PY]) and the period at-risk considered could be from 2 weeks till 6 months for AESI, and 12 months for meningitis.

Table 6 provides an estimation of the 95% CIs based on:

- A sample of 10,000 children per group (either 10,000 in the 6-12 weeks group, or 10,000 in the 5-17 months group) where the RTS,S/AS01_E vaccine will be implemented;
- Different numbers of detected events (for the less frequent events): 1, 3 or 5 events;
- Different risk periods following dose administration (with censoring to one month for the two first doses).
- A follow-up corresponding to the risk period after the virtual dose 4.

For example, the 95% CI around an observed incidence of 25.2 per 100,000 PY (corresponding to 1 event detected, in a risk period of 6 weeks following each dose [censored at the administration of the following dose], based on 10,000 subjects) will be [0.6, 140.2]. Other assumptions are displayed in **Table 6**.

CONFIDENTIAL

115055 (EPI-MALARIA-002 VS AME)
Protocol Amendment 7 Final

Table 6 **Estimation of the lower (LL) and upper (UL) limits of observed incidences of events following dose administration based on 10,000 subjects, different numbers of detected events, and different risk periods**

No. of events	Period at risk	Total person-years	Incidence (in 100,000 PY)	LL (in 100,000 PY)	UL (in 100,000 PY)
Events in different at-risk periods following dose administration (per age group)					
1	2 weeks	1538.46	65.0	1.6	362.2
1	6 weeks	3974.36	25.2	0.6	140.2
1	3 months	6666.67	15.0	0.4	83.6
1	6 months	11666.67	8.6	0.2	47.8
1	12 months	21666.67	4.6	0.1	25.7
3	2 weeks	1538.46	195.0	40.2	569.9
3	6 weeks	3974.36	75.5	15.6	220.6
3	3 months	6666.67	45.0	9.3	131.5
3	6 months	11666.67	25.7	5.3	75.1
3	12 months	21666.67	13.8	2.9	40.5
5	2 weeks	1538.46	325.0	105.5	758.4
5	6 weeks	3974.36	125.8	40.8	293.6
5	3 months	6666.67	75.0	24.4	175.0
5	6 months	11666.67	42.9	13.9	100.0
5	12 months	21666.67	23.1	7.5	53.9

Note: 95% confidence interval limits are computed using the Poisson exact method [Ulm, 1990].

In addition, these incidences will be estimated, using the data collected for both active and enhanced hospitalisation surveillances, for all children less than 5 years of age during the study. [Table 7](#) provides an estimation of the 95% CIs for the surveillances for all children less than 5 years of age based on:

- A birth cohort of 11,500 children;
- A follow-up of 2 years (for the enhanced hospitalisation surveillance, before the start of the EPI-MAL-003 study);
- Different numbers of detected events (for the less frequent events).

CONFIDENTIAL115055 (EPI-MALARIA-002 VS AME)
Protocol Amendment 7 Final

For example, the 95% CI around the observed incidence of 21.7 per 100,000 PY (25 events detected) will be [14.1, 32.1]. Other assumptions are displayed in [Table 7](#).

Table 7 Estimation of the lower (LL) and upper (UL) limits of observed incidences of events among all children less than 5 years of age based on 11,500 birth cohort, and different numbers of detected events

No. of events	Period at risk	Total person-years	Incidence (in 100,000 PY)	LL (in 100,000 PY)	UL (in 100,000 PY)
Events in all children < 5 years during a follow-up of 2 years					
1	2 years	115000	0.9	0.0	4.8
5	2 years	115000	4.3	1.4	10.1
25	2 years	115000	21.7	14.1	32.1
50	2 years	115000	43.5	32.3	57.3

Note: 95% confidence interval limits are computed using the Poisson exact method [[Ulm](#), 1990].

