The EPI-MAL-002 study started in Q4 2015 and will last for approximately 5 years (depending on recruitment timelines). EPI-MAL-003 *started in Q1 2019* when the vaccine *became* available in the study sites that are exposed clusters after its implementation according to WHO guidelines in the framework of the MVIP (first vaccine introduction *was* foreseen in 2018, see section 9.2).

(Amended 5 May 2020)

In parallel with both EPI-MAL-002 and EPI-MAL-003, a third study (EPI-MAL-005) is conducted to measure malaria transmission intensity (MTI) and other malaria control interventions at community level in the study site areas. This study began in Q4 2014, at the first malaria transmission peak season in the West African sites with peak malaria transmission in the second half of the year, and will run through the completion of EPI-MAL-003. It is taking place in similar if not identical settings as EPI-MAL-002 and EPI-MAL-003.

Finally, describing the overall morbidity and mortality in this population is thought to have broader utility beyond these malaria studies, and could serve as baseline data for other disease control and prevention studies.

CONFIDENTIAL115055 (EPI-MALARIA-002 VS AME)
Protocol Amendment 7 Final**8. RESEARCH QUESTION AND OBJECTIVES****8.1. Co-primary objectives**

- To estimate the incidence of AESI², and of other AE leading to hospitalisation or death, in children, prior to implementation of RTS,S/AS01_E.
- To estimate the incidence of aetiology-confirmed meningitis, in children, prior to implementation of RTS,S/AS01_E.

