- Two sites in Malawi have fulfilled the criteria of the study feasibility assessment and were planned to initiate the EPI-MAL-002 study in Q1-Q2 2018. Considering the RTS,S/AS01_E vaccine implementation date in Malawi, currently planned in October 2018, the baseline data that might be collected in

CONFIDENTIAL115055 (EPI-MALARIA-002 VS AME)
Protocol Amendment 7 Final

Malawi in the EPI-MAL-002 study would be too limited to be relevant for the before/after comparisons in this country. Therefore, GSK, in agreement with the WHO, decided to focus the conduct of the EPI-MAL-002 study in Ghana and Kenya, not initiating the study in Malawi, and partially compensating the expected sample size from Malawi sites by using the high recruitment observed from sites in Kenya (Kombewa) and Ghana (Kintampo) and extending recruitment in Ghana (Navrongo).

- EPI-MAL-003 study sites: as currently planned in the MVIP and according to WHO guidance, 4 study sites (corresponding to 4 clusters of the MVIP) in each of the 3 countries selected for the RTS,S/AS01_E pilot implementation programme (12 study sites/clusters in total) are planned to be part of EPI-MAL-003: 2 of them should become exposed clusters and 2 of them should become unexposed clusters (see [Annex 3](#) for definitions of exposed and unexposed clusters). In order to allow the before-after comparison of study endpoints and according to WHO guidance, study sites from Ghana and Kenya included in the EPI-MAL-002 should become study sites in EPI-MAL-003 which will be exposed clusters.
- EPI-MAL-005 study sites: being an ancillary study to EPI-MAL-002 and EPI-MAL-003 studies, EPI-MAL-005 is/will be conducted in study sites conducting EPI-MAL-002 and/or EPI-MAL-003.
- Of note, all study sites are submitted to a comprehensive scientific and operational study site assessment conducted by GSK, which will determine study feasibility in those sites. Exposed and unexposed clusters will be comparable in terms of malaria transmission, health facilities level, geographical region and population size.
- A replacement strategy has also been elaborated in case one or more of the sites conducting EPI-MAL-002 cannot participate in EPI-MAL-003. It could consist in extending the recruitment period in the remaining sites (depending on vaccine implementation strategy).

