9.2.1. Study population

The study population is defined as those children living in the study areas who are < 5 years old.

Following SAGE/MPAC recommendations, sites with moderate-to-high transmission of malaria have started enrolment. In order to reach a birth cohort of about 17,250 children per year (with about 11,500 children per year where the RTS,S/AS01_E vaccine will be implemented), other sites in SSA settings with moderate-to-high transmission of malaria, from the 3 countries where the RTS,S/AS01_E vaccine will be implemented (see Section [9.2](#)), were added to the already defined study sites.

The assumption of such a birth cohort was done to allow recruitment of about 30,000 children in active surveillance in 16 months, with about 20,000 children enrolled where the RTS,S/AS01_E vaccine will be implemented.

Although participation rates are thought to be high in these study sites, taking into account the potential refusal of parents/LARs for their children to join the study, the

CONFIDENTIAL

115055 (EPI-MALARIA-002 VS AME)
Protocol Amendment 7 Final

targeted number of 30,000 children to be enrolled into active surveillance is feasible. Among the 30,000 children recruited for active surveillance with about 20,000 children enrolled where the RTS,S/AS01_E vaccine will be implemented, approximately 15,000 will be part of the 6-12 weeks group (with about 10,000 children enrolled in sites where the vaccine will be implemented) and approximately 15,000 will be part of the 5-17 months group (with about 10,000 children enrolled in sites where the vaccine will be implemented).

In addition to the children enrolled for active surveillance, events of interest will also be collected through the enhanced hospitalisation surveillance.

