#### Management of first year of inclusion:

During the first year of inclusion (i.e. 2016), recruitment was done according to Protocol Amendment 3 where children had to be less than 3 years old with a corresponding census. As a consequence, IR in children < 5 years will be computed after the application on field of the Protocol Amendment 4:

- *Kintampo: 12 June 2017 in AS and 22 May 2017 in EHS*
- *Kombewa: 9 March 2017*
- *Navrongo: subjects entered directly under protocol amendment 4 (25 September 2017)*

The method to compute incidence will be described in a technical annex of the specific Mock TFL for the final analysis.

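### Table 7 assumes 2 years of under-5 surveillance, but the plan's own dates give about 1.6 to 1.8 years on average, so the stated precision is somewhat too favourable

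*Protocol*

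**What the plan says.** Table 7 in Protocol 9.5 covers the secondary analysis population of the co-primary endpoints: all children under 5, from active surveillance and enhanced hospitalisation surveillance (EHS) together (Protocol 9.7.5.1, SAP 6.9.1). Its two inputs are "A birth cohort of 11,500 children" and "A follow-up of 2 years (for the enhanced hospitalisation surveillance, before the start of the EPI-MAL-003 study". Total person-time is 115,000 PY, and "95% confidence interval limits are computed using the Poisson exact method". The worked example reads: "the 95% CI around the observed incidence of 21.7 per 100,000 PY (25 events detected) will be [14.1, 32.1".

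Other sections bear on these inputs:

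- **Origin of the 11,500.** Protocol 9.2.1 gives a target birth cohort of about 17,250 a year, "with about 11,500 children per year where the RTS,S/AS01_E vaccine will be implemented". Sites in the three implementation countries were added to reach it.
- **Malawi.** Protocol 9.2 records that the two planned Malawi sites were not opened, "partially compensating the expected sample size from Malawi sites" through high recruitment at Kombewa and Kintampo and longer recruitment at Navrongo.
- **Sites analysed.** SAP 6.1 leaves Kombewa, Kintampo and Navrongo. Burkina Faso is excluded.
- **Start of the under-5 window.** SAP 6.9.3.3 starts it when Amendment 4 was applied in the field, because children were previously recruited only below 3 years. The dates are 9 March 2017 for Kombewa, 22 May 2017 (EHS) and 12 June 2017 (active surveillance) for Kintampo, and for the third site "Navrongo: subjects entered directly under protocol amendment 4 (25 September 2017".
- **End of EHS.** Protocol 9.1 and 9.2.4 end it at the start of EPI-MAL-003. Protocol 7.4 says "EPI-MAL-003 *started in Q1 2019* when the vaccine *became* available in the study sites that are exposed clusters".

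**The concern.** Table 7 fixes its own window: two years, ending before EPI-MAL-003. The SAP's latest start date is only about 15 to 18 months before the stated EPI-MAL-003 start, so the two years cannot hold at every site. The birth cohort in the table was also left unchanged when the list of implementation sites shrank.

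Table 7 and its example are the only stated precision for the under-5 rates. If person-time is overstated, a reader is led to expect tighter intervals for the background rates than the plan can provide.

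**Working it through.** **1. Reproduce the stated figures.** PY = 11,500 births a year × 5 one-year age bands × 2 years = 115,000. For k events the exact Poisson limits are LL = χ²(0.025; 2k) / (2·PY) and UL = χ²(0.975; 2k+2) / (2·PY). Per 100,000 PY:

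- k = 1: 0.9 [0.0, 4.8]
- k = 5: 4.3 [1.4, 10.1]
- k = 25: 21.7 [14.1, 32.1]
- k = 50: 43.5 [32.3, 57.3]

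All four rows match Table 7. The arithmetic is correct; the question is whether the inputs hold.

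**2. Window length by site.** Time runs from the SAP start date to the start of EPI-MAL-003. Q1 2019 is taken as a range, 1 January to 31 March 2019. Years = days / 365.25.

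| Site | Start | To 1 Jan 2019 | To 31 Mar 2019 |
|---|---|---|---|
| Kombewa | 9 Mar 2017 | 663 d = 1.82 | 752 d = 2.06 |
| Kintampo (EHS) | 22 May 2017 | 589 d = 1.61 | 678 d = 1.86 |
| Navrongo | 25 Sep 2017 | 463 d = 1.27 | 552 d = 1.51 |
| Equal-weight mean | | 1.57 | 1.81 |

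With Kintampo's active-surveillance date (12 June 2017) the mean is 1.55-1.79, a shift of 0.02 years.

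Equal weighting is an assumption, because no site population sizes are given. It does not drive the direction. At 1 January 2019 no site has reached 2 years, so no weighting can. At 31 March 2019, even with Navrongo given no weight, Kombewa would need a share w with 2.059w + 1.856(1 − w) = 2, so w is about 71%.

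**3. Person-years with 11,500 kept.** 11,500 × 5 = 57,500 children under 5. Using the unrounded means (1.565 and 1.809), PY is 89,995 to 104,006, or 78% to 90% of 115,000.

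**4. Effect on the intervals.**

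| Case | 115,000 PY (stated) | 104,006 PY | 89,995 PY |
|---|---|---|---|
| 25 events | 21.7 [14.1, 32.1] | 24.0 [15.6, 35.5] | 27.8 [18.0, 41.0] |
| 1 event, upper limit | 4.8 | 5.4 | 6.2 |
| About the same incidence | 25 events: 21.7 [14.1, 32.1] | 23 events: 22.1 [14.0, 33.2] | 20 events: 22.2 [13.6, 34.3] |

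At a fixed event count the interval widens by 115,000 / PY, that is 11% to 28%. At about the same incidence its width goes from 32.1 − 14.1 = 18.0 to 33.2 − 14.0 = 19.2 or 34.3 − 13.6 = 20.7, about 7% to 15% wider.

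**5. What would restore 115,000 PY.** Either a mean window of 2 years, which with equal weights needs EHS to close around 8 June 2019, or a larger birth cohort. The latter is 115,000 / (5 × 1.809) ≈ 12,700 to 115,000 / (5 × 1.565) ≈ 14,700 births a year across the three sites.

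**6. The birth cohort.** No section gives a birth cohort for Kombewa, Kintampo, Navrongo or the planned Malawi sites, so this part cannot be calculated. Higher or longer recruitment can enrol more children into active surveillance, but it adds no births to a catchment area. Under SAP 6.9.3.3 the under-5 denominator is the census population.

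**The case against.** **The end date is not site-specific.** Q1 2019 is one study-level date. Protocol 9.9 says that the EPI-MAL-003 start might vary with vaccine implementation in each country, and EPI-MAL-003 also includes Malawi, so the first start need not be in Kenya or Ghana. This stands as a limit on size: a later closure at a site shrinks the gap. But no other date is given, and if later dates apply, Table 7 should rest on them.

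**Person-time could run longer.** Protocol 9.7.5.2.1 lets children contribute until study end or age 5, and read literally that could exceed 2 years. Table 7, however, sets its own window before EPI-MAL-003. Once EHS closes, cases outside active surveillance are no longer captured.

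**Little depends on the table.** No hypothesis or power calculation uses it, final intervals will use observed events and census person-time, and the site start dates were added in SAP Amendment 2 (March 2022), after EHS had closed on the dates used here. This stands: the point is about an accurate statement of precision and changes no design decision.

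**Stronger readings.** A reader might infer that the three sites fall short of 11,500 births, perhaps by Malawi's share as two of five equal sites. The documents do not support that. They give no site figures, and Protocol 9.2.1.1 calls the parent figure of 17,250 conservative because births are rising. A reader might also infer that no site reaches 2 years. Kombewa does if EHS closed there on or after 9 March 2019.

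**Conclusion.** The point holds for the length of the window. On the SAP start dates and the only stated EPI-MAL-003 start, the mean surveillance time is 1.57-1.81 years rather than 2, and person-time is about 90,000-104,000 rather than 115,000. The stated intervals are too narrow by 11% to 28% at a fixed event count, and by less at the same incidence. That is a moderate overstatement.

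The figures assume equal-sized sites, EHS closing at all three sites within Q1 2019, and 11,500 births a year.

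On the birth cohort the conclusion is weaker: 11,500 was a target for implementation sites in three countries, was kept after Malawi was dropped, and is unsupported for the three analysed sites. It is not shown to be wrong, and the size of any shortfall cannot be derived from the documents.

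**What to change.** Recompute Table 7 and the worked example from the under-5 census counts of Kombewa, Kintampo and Navrongo. Multiply each count by that site's surveillance time, from its SAP 6.9.3.3 start date to its actual EHS closure, and restate the person-years and limits. Give the site counts and the start and closure dates beside the table, so that the 11,500 and the 2 years are either confirmed or replaced.

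The cost is one recalculated table and a revised example. Stated precision is likely to be somewhat less favourable. No additional children or data collection are needed.
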